Vestibular Intervention Via Portable Electrical Stimulator (VIPES)

NCT04968197

August 18, 2023

IRB Minimal Risk Protocol Template

General Study Information

Principal Investigator: [name]

Study Title: Vestibular Intervention via Portable Electrical Stimulator (VIPES)

Protocol version number and date: Version 2 and August 18th, 2023

Research Question and Aims

Hypothesis:

The efficacy of stochastic galvanic vestibular stimulation to improve balance and gait performance in individuals diagnosed with mild traumatic brain injury or experience vestibular disorders causing dizziness, impaired balance, and altered coordination.

Aims, purpose, or objectives:

To develop a wearable portable stimulator to stimulate the vestibular system and produce immediate improvements in balance, gait, and overall vestibular function for patients with balance disorders.

Background (*Include relevant experience, gaps in current knowledge, preliminary data, etc.*):

The vestibular system is an essential element of human balance, which is critical to proper stance and gait. An impaired vestibular system can cause debilitating dizziness or loss of balance leading to dangerous falls and an inability to perform normal activities of daily living. Vestibular dysfunction is both a hallmark of acute traumatic brain injury (TBI) and also a long-term problem with considerable quality of life effects for those experiencing mild TBI (mTBI). Often times, this dysfunction is due to a reduction in the signal from the vestibular system to the brain, resulting in a misrepresentation of the balance state of the individual with dysfunction. Recent and ongoing research has demonstrated that by boosting the signals produced from the vestibular system, these balance issues and the symptoms that go along with them can be alleviated.

To date, the War on Terror has claimed over 50,000 US casualties, many of which stem from an increase in wartime blast threats from improvised explosive devices (IEDs). Between 2000 and 2018, US Military personnel had experienced 383,947 cases of TBI, 315,897 of which were classified as mild TBI [1]. Nearly 30% of soldiers that are diagnosed with mild traumatic brain injury or worse experience vestibular disorders causing dizziness, impaired balance, and altered coordination that prevent their performance in reparative physical therapy, impede return to duty, and significantly reduce quality of life. Similarly, as many as 35% of civilian adults aged 40 years or older in the United States (~69 million Americans) have experienced some form of vestibular dysfunction with a further 4% (8 million) of American adults reporting a chronic problem with balance. Symptoms of chronic imbalance can have a significant impact on the ability of a disabled person to perform one or more activities of daily living (ADL), a term used for basic necessities such as bathing, dressing, or simply getting around inside the home.

Giving attention to this prevalent problem among warfighters and civilians alike, researchers have attempted to restore balance through vestibular implants, vibrotactile feedback, tongue placed biofeedback, and vibrating

insoles. Of these, the vestibular implant is the only one directly targeting the vestibular system. However, the invasive nature of such implants is unwarranted for acute symptoms and is highly risky for an older population that is more susceptible to surgical complication. The remaining approaches indirectly stimulate the central nervous system (CNS) as opposed to producing actual vestibular sensation. Further, many of the symptoms brought on by mTBI are acute in nature, where the vast majority of patients see improvement over a specific amount of time. Thus, implants, while highly beneficial for those with chronic vestibular dysfunction, simply do not fit a need for the vast majority of cases, revealing an immediate and significant need for a means to provide the same vestibular dysfunction correction as an implant via a comfortably worn, non-invasive device.

Recent work has focused on non-invasive electrical stimulation of the vestibular system, historically called galvanic vestibular stimulation (GVS), including use of electrical signals comprising filtered random noise, known as stochastic vestibular stimulation (SVS). These techniques promise a device that could address a loss of vestibular function and improve balance without the aforementioned drawbacks of other systems and the side effects of pharmacologic therapy. Complimentary, prior work performed in Aerospace Medicine and Vestibular Research Laboratory at Mayo Clinic Arizona has demonstrated several unique modes of transcutaneous GVS to: 1) induce a controlled sense of motion when none is present (IRB#: **06-005443**), 2) provide directional vestibular cueing (IRB#s: **09-003815, 18-005564, 19-003257**), and 3) mitigate the debilitating effects of motion sickness stemming from decoupling of the vestibular and visual cues (IRB#s: **11-007718, 20-005763**) [2, 3]. Significant work by others has shown that introduction of stochastic vestibular stimulation creates a stochastic resonance effect, enhancing the diminished vestibular response in subjects with history of blast injury and mTBI. While SVS can help many patients with mTBI related vestibular impairment, other GVS stimulation modes may also be required depending on the location and severity of the injury and the nature of the activities being undertaken. Thus, a multi-modal vestibular stimulation approach is paramount to addressing the multi-variant problem of vestibular dysfunction and reaching the vast majority of patients that experience mTBI related symptoms. The proposed Vestibular Intervention via Portable Electrical Stimulator (VIPES) system (Figure 1) is a small, lightweight device able to deliver SVS using a comfortable electrode set on the back of the head as well as other proven modes of GVS related vestibular correction when required to mitigate motion sickness or provide auxiliary vestibular cueing.

[figure not shown]

Figure 1: VIPES includes a disposable set of electrodes located behind the ears, which can be integrated into a low cost, comfortable, multi-use hearing aid style device that fits behind the ear and reports head position/motion for multi-modality control, and a small electronics / battery module that comfortably hangs down the users neck.

References:

In this repeated-measures design, each patient will be tested in a “*Control*”, or baseline condition, and a pre-determined stimulation level of “*Stochastic Vestibular Stimulation (SVS)*” up to 1mA. In the *Control* condition: the entire testing will be conducted with the system worn but without SVS application (i.e., 0mA). The patient will be instrumented with electrodes without turning on the SVS device throughout the testing. In the SVS condition: The SVS device will be active throughout the testing at the respective current level. The test will be performed for a singular, pre-determined, GVS amplitude up to 1mA. The order of the conditions will be randomized across subjects. The details of testing (single visit) are summarized below.

Equipment:

The VIPES system that provides SVS is a small wearable device in order to improve the function of an individual’s vestibular system that has been adversely affected their balance due to head injuries and mild TBI. In particular, VIPES is designed to provide electrical stimulus comprising random noise in a low frequency band (0 to 5Hz maximum) below the level of perception by the subject. The VIPES system consists of the four electrodes (two behind each ear) similar to our commercial galvanic stimulator (Good Vibrations Engineering Ltd, King City, ON; used in the previous IRB approved projects – IRB #s: 20-005763, -19-003257, 18-005564, 14-003906, 11-007718, 09-003815). The stimulator can bidirectionally deliver the electrical stimulation and receive information about the amplitude delivered accounting for skin impedance. Bertec Portable Essential’s dual-balance plate balance system (previously IRB approved in IRB 20-005763) used for balance testing is clinically used in Mayo Clinic Arizona.

Testing:

Following documentation of consent for study participation, participants will complete pre-testing questionnaires and medical history evaluations. Subjects will don the VIPES device and the research team will verify the system is set to 0mA and participants will then be given a direction and timeframe to walk in the Mayo Clinic space for up to 10 minutes before returning to the laboratory, as a means of establishing baseline gait, balance, stability, and pace to be measured by an incorporated accelerometer (sway score; deg/s). Once returned, participants will be allotted a 5-minute resting period prior to beginning the ‘*Condition*’ testing.

Subjects will complete a series of balance tests to establish and describe a range of balance performance. The Modified Clinical Test of Sensory Interaction and Balance (mCTSIB) [4], and COBALT Balance test [5] are measures of standing balance that increase in difficulty. These metrics will be included for the rationales noted below, but also to better describe the wide ability of balance function in individuals with balance disorder.

Subjects will be randomized for balancing testing condition order and will complete the mCTSIB and COBALT with the system providing a known amount of electrical stimulus, as well as with the system providing 0mA, but will be blinded for which condition is taking place. Participants will be permitted to leave and walk normally about the premises with the VIPES system now provided the known-stimulation dose. A member of the investigational team will accompany the subjects for the duration of their walking. Subjects will return after ~30-45 mins and will be allotted an additional 5-minute resting period. Subjects will complete the mCTSIB and COBALT balance tests with the system delivering stimulation. Once completed, the VIPES system will be

removed and participants will answer the Post-Testing Questionnaires before finishing the study day and being provided remuneration. The details of testing are summarized as follows:

Visit:	Duration
Consent & Pre-Testing Questionnaire(s) 
 Post-concussion symptoms scale Demographics & Medical History 	10 mins
Baseline Walk 
 Participants will walk with the system at 0mA, as is normal, for up to 10 minutes to establish baseline gait Subject will rest for approximately 5 minutes. 	15 mins
COBALT Balance Test: Device: Bertec Portable Essential's dual-balance plate balance system (https://www.bertec.com/bertec-balance-advantage-systems) Rationale: COBALT is a balance test commonly used to evaluate individuals post-concussion. This test protocol places high demand on the visual and vestibular systems that is not provided by traditional balance tests. These higher demand conditions improve sensitivity in detecting balance dysfunction in those post-concussion. The test will be performed for a given SVS amplitude up to 1mA and 0mA, and will be randomized for each subject. Two 20-seconds trial for each of the following conditions/surfaces: On Firm Surface: 
 Head Shake Visual Motion Sensitivity On Foam Surface: 
 Head Shake Visual Motion Sensitivity 	10 mins
Modified Clinical Test of Sensory Integration on Balance (mCTSIB): Device: Bertec Portable Essential's dual-balance plate balance system (https://www.bertec.com/bertec-balance-advantage-systems) Rationale: mCTSIB is a balance test commonly used to evaluate individuals of all ages post-concussion. This test protocol assesses how well an individual uses sensory input when one or more sensory systems are	10 mins

compromised. This protocol is commonly used to evaluate individuals post-concussion to describe static balance ability.

The test will be performed for a given SVS amplitude up to 1mA and 0mA, and will be randomized for each subject.

Three 10-second trials for each of the following conditions:

- Standard (eyes open on firm surface)
- Proprioception (eyes closed on firm surface)
- Vision (eyes open on foam surface)
- Vestibular (eye closed on foam surface)

SVS Condition Walk	50 mins
Repeat mCTSIB and COBALT	20 mins
Post-testing Questionnaires:	5 mins

Subject Information

Target accrual is the proposed total number of subjects to be included in this study at Mayo Clinic. A “Subject” may include medical records, images, or specimens generated at Mayo Clinic and/or received from external sources.

Target accrual: 40 participants

Subject population (adults, groups): Patients – 1) diagnosed with a balance disorder and/or having sustained a concussion and/or mild traumatic brain injury (mTBI), 2) Currently being evaluated at Mayo Clinic Arizona, 3) self-reported imbalance,

Inclusion Criteria: For our purposes, participants must be able to consent to participate themselves and be 18 to 70 years of age and must be able to attend in-person sessions at the Mayo Aerospace Medicine and Vestibular

Research Laboratory in Scottsdale, AZ. No racial/ethnic groups will be excluded, although all participants must be fluent speakers of English

Exclusion Criteria: 1) Presence of peripheral vestibulopathy (cleared by Dix-Hallpike, vHIT as part of clinical evaluation), 2) women who are pregnant, and 3), inability to complete testing (e.g., severe symptom burden, inability to stand unassisted).

Biospecimens

Collection of blood samples. When multiple groups are involved copy and paste the appropriate section below for example repeat section b when drawing blood from children and adults with cancer.

a. **From healthy, non-pregnant, adult subjects who weigh at least 110 pounds.** For a minimal risk application, the amount of blood drawn from these subjects may not exceed 550ml in an 8 week period and collection may not occur more frequently than 2 times per week.

Volume per blood draw: N/A ml

Frequency of blood draw (e.g. single draw, time(s) per week, per year, etc.) N/A

b. **From other adults and children considering age, weight, and health of subject.** For a minimal risk application, the amount of blood drawn from these subjects may not exceed the lesser of 50 ml or 3 ml per kg in an 8 week period, and collection may not occur more frequently than 2 times per week.

Volume per blood draw: N/A ml

Frequency of blood draw (e.g. single draw, time(s) per week, per year, etc.) N/A

Prospective collection of biological specimens other than blood: N/A

Review of medical records, images, specimens

Check all that apply (data includes medical records, images, specimens).

Only data that exists before the IRB submission date will be collected.

Date Range for Specimens and/or Review of Medical Records:

Examples: 01/01/1999 through 12/31/2015, or all records through mm/dd/yyyy.

Note: The Date Range must include the period for collection of baseline data, as well as follow-up data, if applicable.

The study involves data that exist at the time of IRB submission **and** data that will be generated after IRB submission. Include this activity in the Methods section.

Examples

- The study plans to conduct a retrospective chart review and ask subjects to complete a questionnaire.
- The study plans to include subjects previously diagnosed with a specific disease and add newly diagnosed subjects in the future.

The study will use data that have been collected under another IRB protocol. Include in the Methods section and enter the IRB number from which the research material will be obtained. *When appropriate, note when subjects have provided consent for future use of their data and/or specimens as described in this protocol.*

Enter one IRB number per line, add more lines as needed

Data Specimens Data & Specimens _____

Data Specimens Data & Specimens _____

Data Specimens Data & Specimens _____

Data Analysis

Power analyses may not be appropriate if this is a feasibility or pilot study, but end-point analysis plans are always appropriate even if only exploratory. Provide all information requested below, or provide justification if not including all of the information.

Data Analysis Plan:

We will use repeated measures ANOVA to examine changes in balance performance during balance testing by measuring sway score (i.e., sway angular velocity, deg/s) across tested levels of GVR amplitude and control condition. Sample size estimates are based on: (1) the expected variability (s^2) in the response parameters, (2) the alpha (α , type I) error level, or probability of incorrectly concluding there is an effect when responses are equivalent, (3) the magnitude of the effects to be detected between the means (μ_1, μ_2), and (4) the certainty (statistical power, $1 - \beta$) with which the effect is to be detected. Sample sizes can be calculated based on the expected standardized differences (Δ) between conditions.

Power Statement:

Standardized mean differences of 0.08 deg/s on firm surface and 0.17 deg/s on foam surface will be considered operationally relevant effect sizes for balance performance comparison based on previous balance testing protocols using the COBALT testing [5]. Based on the equation above, we will have 80% statistical power to detect standardized mean differences (two-sided tests) of 0.08 (firm surface) and 0.17 (foam surface) with an

alpha error level of 0.05 with a sample of 22 participants. A target of at least 30 participants is requested to account for incomplete data sets.

Endpoints

Primary: Our project will deliver a vestibular interventional approach using stochastic vestibular stimulation (SVS) through a small, lightweight, and portable device housed in a body-worn torso strap that feeds into a comfortable electrode set on the back of the head (on the mastoid process) to deliver continuous and dose-specific stimulation to the vestibular system and produce immediate improvements in balance, gait, and overall vestibular function.

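### Test order is randomised without a stated equal split, and the ANOVA names no run term, so any practice or fatigue shift between the two runs would cost power

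*Combined protocol and SAP*

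**What the plan says.** Order is addressed three times under Study Design and Methods.

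- The Protocol paragraph states: "The order of the conditions will be randomized across subjects".
- Testing states: "Subjects will be randomized for balancing testing condition order". In context, the word balancing there refers to balance testing and not to an allocation method.
- The visit table repeats, separately under COBALT and under mCTSIB: "The test will be performed for a given SVS amplitude up to 1mA and 0mA, and will be randomized for each subject".

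None of these gives blocks, counterbalancing or a sequence ratio.

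The Data Analysis Plan is the only description of the model: "We will use repeated measures ANOVA to examine changes in balance performance during balance testing by measuring sway score", with the comparison made "across tested levels of GVR amplitude and control condition". It mentions no run, order or sequence term.

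After the SVS walk, both tests are done once more: "Subjects will complete the mCTSIB and COBALT balance tests with the system delivering stimulation". That run is always last and always under SVS.

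**The concern.** Each participant performs the same COBALT and mCTSIB tasks under both conditions in one visit. The visit table schedules a walk and a rest before the first run, but no practice trial. A change from first to second run is therefore plausible, whether from learning the foam, head-shake and visual-motion tasks or from tiring. This is an ordinary period effect. It needs no persistence of stimulation after switch-off, so a washout would not remove it.

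The shift is added to the SVS minus 0 mA difference in participants who receive SVS second and subtracted in those who receive it first. A model without a run term treats that spread as residual error. At stake is the power claimed for 22 participants, and also the estimate itself if chance produces clearly unequal orders.

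**Working it through.** **The plan's own figure.** The Power Statement claims 80% power, two-sided alpha 0.05, with 22 participants, for "Standardized mean differences of 0.08 deg/s on firm surface and 0.17 deg/s on foam surface". Taken as truly standardized paired differences, n = ((1.960 + 0.842)/d)² gives 1,227 for d = 0.08 and 272 for d = 0.17, so 22 does not reproduce. That is a separate defect. To examine order at all, I read 0.08 and 0.17 as raw deg/s and back-solve the SD. A paired t-test with n = 22 has 80% power at an effect of 0.626 SD, so the SD of the within-person difference is 0.08/0.626 = 0.128 (firm) and 0.17/0.626 = 0.271 (foam). Neither SD is stated in the plan.

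**Model.** For each participant, D = SVS minus 0 mA = τ + s·π + e. Here s = +1 if SVS is second and −1 if first, π is the shift from run 1 to run 2, and e has the SD above. There is no carryover. The documents give no π, so I use 0.04, 0.08 and 0.12 deg/s. Simple randomisation is also an assumption, because no method is named.

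**Error term.** With near-equal orders and no run term, Var(D) rises from SD² to about SD² + π². On firm, SD² = 0.128² = 0.0164:
- π = 0.04: (0.0164 + 0.0016)/0.0164 = 1.10
- π = 0.08: (0.0164 + 0.0064)/0.0164 = 1.39
- π = 0.12: (0.0164 + 0.0144)/0.0164 = 1.88

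On foam, SD² = 0.271² = 0.0734, and the ratios are 1.02, 1.09 and 1.20.

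**Power by simulation.** Columns 3 to 5 use the paired t-test without a run term under simple randomisation (for two conditions this is the same test as the repeated measures ANOVA). The last column uses equal orders and a run term (n − 2 df).

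| Surface | n | π = 0.04 | π = 0.08 | π = 0.12 | Equal orders + run term |
|---|---|---|---|---|---|
| Firm | 22 | 76% | 66% | 53% | 80% |
| Foam | 22 | 79% | 77% | 73% | 80% |
| Firm | 30 | 89% | 80% | 67% | 91% |
| Firm | 40 | 96% | 91% | 80% | 97% |

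Both parts of the remedy matter. On firm at n = 22 and π = 0.08, equal orders without the run term give about 68%. The run term under simple randomisation gives about 78%.

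**Uneven orders.** Given the realised split, the estimate moves by π × (nA − nB)/n, where nA is the number with SVS second and nB the number with SVS first. Under simple randomisation at n = 22:
- P(exactly 11:11) = 17%
- P(8:14 or worse) = 2 × P(X ≤ 8; 22, 0.5) = 0.286
- P(7:15 or worse) = 0.134

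At 8:14 with π = 0.08 the estimate moves 0.08 × 6/22 = 0.022 deg/s, which is 0.022/0.08 = 27% of the firm target. Averaged over all randomisations the simulated bias is about zero and the type I error about 5%.

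**The case against.** **Silence is not a decision.** The plan does not rule out a balanced order list, and one sentence on the ANOVA is not a full model specification. This stands: the supportable statement is that balancing and a run term are not specified.

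**Randomisation already protects validity.** A reader might infer that the treatment comparison is biased. The documents do not support that. Random order keeps the estimate unbiased and the type I error near 5% over randomisations, and the displacement exists only given an uneven realised split. Nor is that displacement as large as the target: the worked case is about a quarter of it, and it needs both an 8:14 split and a shift as large as the whole firm effect. At 10:12 the same shift moves the estimate by 0.08 × 2/22 = 0.007 deg/s, or 9% of target.

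**The shift is assumed.** No practice or fatigue effect is reported. Testing per condition is short: COBALT has 4 tasks × 2 trials × 20 s = 160 s and mCTSIB 4 × 3 × 10 s = 120 s, so marked fatigue is not obvious. This stands. A shift of 0.04 costs about 4 points on firm and 1 on foam at n = 22.

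**More participants are planned.** A reader might also infer that the trial will miss 80% power. At n = 30, firm power is still about 80% with a 0.08 shift. At the accrual target of 40 under Subject Information, it is 80% or more across the range shown. However, the Power Statement rests its claim on 22 participants and requests 30 to cover incomplete data, so the n = 22 figures bear directly on that claim.

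**Conclusion.** The point holds as a question of efficiency and specification, not of validity. Under the stated assumptions, a run-to-run shift would reduce firm-surface power at n = 22 from about 80% to between 76% and 53%, and foam-surface power to between 79% and 73%. At n = 40 the loss leaves firm power at 80% or above. An 8:14 split or worse has a 29% chance at n = 22 under simple randomisation, and at 8:14 a 0.08 shift would displace the firm estimate by 0.022 deg/s. These figures rest on reading the targets as raw deg/s, on back-solved SDs, on simple randomisation and on shifts that the documents do not give. What does not depend on those values is the direction: any non-zero shift inflates the error term of the stated model. Equal orders with a run term remove that cost almost for free, and if there is no shift, power is still about 80% at n = 22.

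**What to change.** Allocate condition order 1:1 in permuted blocks. For the two randomised runs, fit run (first or second) as a fixed effect next to stimulation, with participant as the blocking factor. Because order randomisation is stated separately under COBALT and mCTSIB, say whether one order applies to both tests, and define run within each test.

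Keep the post-walk run out of this comparison and state how it will be analysed. It is always under SVS and always last, so balancing the first two runs does not remove its confounding with order.

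The cost is a blocked order list, one model term and one error degree of freedom, with no added participants, visits or procedures.

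### No interval is stated between the randomised SVS and 0 mA runs, and the ANOVA has no period or sequence term, so an SVS after-effect would bias the comparison unseen

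*Combined protocol and SAP*

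**What the plan says.** The design is set out under Study Design and Methods (Protocol and Testing). Each patient serves as their own control, with one pre-determined SVS amplitude compared with 0 mA. On order: "The order of the conditions will be randomized across subjects". On timing: "The details of testing (single visit) are summarized below". Patients "will complete the mCTSIB and COBALT with the system providing a known amount of electrical stimulus, as well as with the system providing 0mA", blinded to which condition is running.

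Two rests are specified. After the baseline walk, "participants will be allotted a 5-minute resting period prior to beginning the" condition testing. After the later walk under stimulation: "Subjects will return after ~30-45 mins and will be allotted an additional 5-minute resting period". A third test run follows that second rest, with stimulation only: "Subjects will complete the mCTSIB and COBALT balance tests with the system delivering stimulation". No interval is given between the randomised SVS and 0 mA runs. The visit timetable lists COBALT (10 min), mCTSIB (10 min) and then the SVS walk, with nothing between them.

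The Data Analysis Plan is a repeated measures ANOVA of sway score across GVS amplitude and control. It names no period, sequence or carryover term. The Endpoints section expects an immediate improvement. Nothing in the documents addresses how long an effect lasts once the current is off.

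**The concern.** The SVS and 0 mA runs form a two-period crossover within one visit. Randomising the order balances practice and fatigue on average. It does not protect the control run of a patient who has just had SVS. If the stimulus leaves an after-effect in the same direction as its benefit, that control run looks better than a true control and the difference shrinks. An effective stimulus could then look weaker than it is, and the planned model has nothing that would point to the cause. A rebound in the opposite direction would exaggerate the benefit, equally unseen.

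Omitting the order term has a cost even without carryover, because any practice or fatigue effect between the two runs then goes into the error variance.

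**Working it through.** **Inputs.** From the Power Statement: two-sided alpha 0.05, 80% power, n = 22, a target of at least 30, and differences of 0.08 (firm) and 0.17 (foam). From Subject Information: target accrual 40. Assumptions: 1:1 order, one block per condition, and c, the share of the SVS effect that persists into a following 0 mA run. The documents give no value for c.

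**The plan's own figure.** n = 22 does not reproduce if 0.08 and 0.17 are standardised differences; a paired t-test would need 1229 and 274. Read as raw deg/s, n = 22 requires an SD of the paired difference of about 0.08/0.626 = 0.13 (firm) and 0.17/0.626 = 0.27 (foam), which the documents do not give. This is a separate problem. For the present point I take only the effect that has 80% power at n = 22 in a paired t-test, d = 0.626 SDs of the paired difference.

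**Bias.** Patients with 0 mA first have expected difference d. Patients with SVS first have d(1 − c). With balanced order the mean is d(1 − c/2). At c = 0.5 the estimate is 75% of the truth: 0.08 becomes 0.06 and 0.17 becomes 0.1275 deg/s. A larger sample does not change this.

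**Power.** When order is ignored, the gap between the two orders also adds (c·d/2)² to the variance of the difference, so the effective size is d(1 − c/2)/√(1 + (c·d/2)²). At c = 0.5 this is 0.626 × 0.75/√(1 + 0.1566²) = 0.470/1.012 = 0.464.

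| c (assumed) | Effect kept | Power n = 22 | n = 30 | n = 40 |
|---|---|---|---|---|
| 0 | 100% | 80% | 91% | 97% |
| 0.10 | 95% | 76% | 88% | 96% |
| 0.25 | 87.5% | 69% | 82% | 92% |
| 0.50 | 75% | 55% | 69% | 82% |
| 1.00 | 50% | 27% | 35% | 45% |

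The n = 30 and n = 40 columns assume complete data on that number. Simulation at n = 22 gave 68%, 55% and 26% at c = 0.25, 0.5 and 1.

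**Where c/2 may be too small.** The timetable gives COBALT and mCTSIB separate rows and says of each that it is run at SVS and at 0 mA. If the condition switches within each test, a patient who starts COBALT at 0 mA ends it under SVS before starting mCTSIB. With the same order in both tests, every mCTSIB 0 mA run then comes after some SVS. If the same share persists across the change of test, the mCTSIB difference shrinks by c rather than c/2.

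**Order term.** Suppose there is no carryover but a period effect of half an SD of the paired difference (assumed). Leaving it in the error multiplies the variance by 1 + 0.5² = 1.25, so d falls to 0.626/√1.25 = 0.560 and power at n = 22 falls from 80% to about 71%.

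**Time.** The COBALT row reads "Two 20-seconds trial for each of the following conditions/surfaces"; with four conditions that is 4 × 2 × 20 = 160 s per run. mCTSIB is 4 × 3 × 10 = 120 s. Both amplitudes take 2 × (160 + 120) = 560 s, or 9.3 min, of recording in a 20-minute block. The later repeat, at one amplitude, is also given 20 minutes.

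**The case against.** The strongest reply is that nothing in the documents suggests persistence. The Background describes a stochastic resonance effect that enhances the vestibular response, the device is active throughout SVS testing, and recorded exposure before a 0 mA run may be only 160 to 280 s. If the effect stops with the current, c is zero and there is no bias. That stands as far as it goes: the size is unknown and the figures above are illustrations. It does not settle the matter, because the documents address onset and are silent on offset.

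A reader might infer three stronger things, and the documents support none of them:

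- That the runs are back to back. The text states no gap but does not exclude one, and staff may pause informally.
- That any after-effect biases toward no difference. That holds only for an after-effect of the same sign.
- That the trial's primary comparison is compromised. No comparison is labelled primary, and the Primary entry under Endpoints describes a device. SVS against 0 mA is nevertheless the contrast that the ANOVA addresses.

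At the accrual target of 40, power stays near 80% even at c = 50%. That is correct, but the estimate is still 25% too small.

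The existing 5-minute rests each follow a walk, and the second precedes a stimulation run, so they are no evidence that 5 minutes is an adequate washout. This also stands.

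**Conclusion.** The concern holds as a gap in design and analysis, not as a demonstrated bias. The interval between the randomised runs is unstated, the run sequence is ambiguous, and the model ignores the order that the trial randomises. If a share c of the effect persists in the same direction, the difference is understated by c/2 under one block per condition and balanced order, and possibly by c for mCTSIB if conditions switch within each test. At an assumed c of 50% the estimate is 25% too small whatever the sample size. Power figures further rest on an effect with 80% power at n = 22, which the plan's stated inputs do not establish.

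**What to change.** 1. State the run sequence: one block per condition, or switching within each test. Specify a fixed rest between the randomised runs. The 5-minute rest already used elsewhere is one example; the study team should justify its length as washout.
2. Include period and sequence (randomised order) in the model, applied to the randomised pre-walk runs. The post-walk run is always under SVS and always last, so it should not be pooled into that comparison. These terms recover precision and make order effects visible. They do not remove carryover, which only the interval can do.
3. Report SVS against 0 mA from first runs only, as a supportive sensitivity analysis. It has low power. With 11 per order and an assumed within-patient correlation r of 0.5 to 0.9, the between-patient SD is 1/√(2(1 − r)) SDs of the paired difference, and power is about 29% down to 10%. A formal carryover test is no substitute: its power is about 6 to 13% at c = 100% under the same assumptions.

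**Cost.** About 5 minutes per rest and one or two degrees of freedom. The rest may not fit in the 20 minutes allotted, because the 9.3 minutes counts recording only and omits set-up, instruction and surface changes. If conditions switch within each test, up to three rests would be needed, and 9.3 + 15 = 24.3 min exceeds the block.
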